2.4.1.5 Data management

Study data on vital signs, patient admissions and adverse outcomes will be extracted on site by Portsmouth and Oxford University Hospitals Trusts and all patient-identifiable information will undergo local pseudo-anonymization. These de-identified data will be held in secure clinical data repositories, which will be subject to additional security checks and only be accessible to relevant members of the research team for the purposes of the study. Data sets for analysis will be generated from the repository, using algorithms developed as part of the HAVEN (ISRCTN12518261) and Missed Care (ISRCTN17930973) projects to link them. All transfers of individual patient data will use secure data transfer protocols.

2.4.2 Consultation stages

2.4.2.1 PPI

We will run focus groups for patients to identify the factors that they believe should be taken into account in designing monitoring protocols.

We will ask them to consider the following questions:

1. What factors influence their thinking on how frequently a patient should be monitored?

- 2. How can clinical staff best communicate to a patient the factors affecting their monitoring frequency and differences they might notice from that of other patients?
- 3. How should monitoring protocols strike a balance between the patient's safety and their inconvenience (e.g. waking from sleep)?
- 4. What can be done in the future to improve the way in which observations are made?
- 5. Is there a difference to be made between how frequently vital signs should be taken and how frequently escalations in care should happen?

Each group will be run by a trained facilitator. The patient groups will also addition be attended by at least one of our PPI representatives. After obtaining appropriate consent from participants, the discussions in each focus group will be audio recorded. The recordings will subsequently be analysed by two further independent assessors. Combining these notes with those from the facilitator, we will undertake a thematic analysis to identify key factors in response to the questions above.

The results of these focus groups will be used to inform the design and refinement of our monitoring protocols. Participants' feedback will also be incorporated into the final report and other publications.

2.4.2.2 Stakeholder engagement (focus groups and interviews)

Early in the project, we will engage with key clinical stakeholder groups (nurses, doctors, healthcare assistants) to identify additional factors to be considered in designing monitoring protocols. We will collect views from these key professional groups though focus groups, interviews, ad-hoc discussion, and facilitated/mediated Twitter Chat sessions. Focus groups will contain a mix of senior and junior staff from each discipline. Nursing staff will form a substantial proportion, as this group is most directly involved in obtaining and responding to vital signs observations. We will ask them to consider the following questions:

- 1. What factors are most important in determining observation frequency?
- 2. What factors are most likely to affect adherence to current monitoring protocols?
- 3. How are "observation rounds" incorporated into current monitoring protocols? Semi-structured discussions (for example, interviews and Twitter Chat sessions) with staff will be structured around topic guides that will be developed/evolved from focus group and observation results.

Towards the end of the project, further focus groups will be held to report our results and proposed observation protocols to key stakeholders. We will address the following questions:

- 1. What are the potential technical barriers to implementing these protocols, given the range of systems for recording vital signs observations (both electronic and paper-based)?
- 2. What are the potential barriers to integrating these protocols into current nursing workflows and workloads?
- 3. What modifications to the protocols could facilitate implementation? In addition, we will revisit areas previously observed to confirm themes identified through these later focus groups.

This mixed methods approach will enable triangulation of the qualitative data collection, developing a richer understanding of the process of patient monitoring. This in turn will enhance the interpretation of the quantitative results from other phases of the project.

Therefore the results of these focus groups will be used to inform the design and refinement of our monitoring protocols. Participants' feedback will also be incorporated into the final report and other publications.

2.4.3 Prospective Observational Study

2.4.3.1 Study setting

The observational study to provide reliable estimates of the nursing work involved in measuring vital signs³ will be undertaken in 16 adult general wards at 4 acute general NHS hospital Trusts. Our 2 core study sites (see above) both use electronic recording for vital signs. We will therefore seek to recruit 2 additional Trusts that retain paper and pen recording.

2.4.3.2 -Sample and recruitment

We will undertake observations on wards of the two study sites and two additional sites recruited from volunteer Trusts within the Wessex region, selected with a view to sampling a variety of approaches to the recording of vital signs and activation of the EWS alerts.

Eligible wards are those classified as adult general (medical / surgical) wards. As there is no generally accepted precise definition of this, we will ask participating Trusts to identify wards against the following criteria:

- Adult (18+) patients. Wards that occasionally admit adolescents of younger age would remain eligible provided this was not a common occurrence.
- ii) Open at weekends with most patients experiencing overnight stays of one day or more
- iii) Ward provides Levels of Care 0, or 0 and 1

Exclusions

- i) Wards which routinely cater for large number of younger people (<18)
- ii) Wards in which a significant proportion of patients require protective isolation
- iii) Wards that are intended to exclusively provide Level 1+ care
- iv) Wards where the risk of acute deterioration is low or where the primary reason for continued hospital stay is not medical / surgical treatment / recovery (e.g. rehabilitation units, other post-acute wards)
- v) Wards where full vital signs measurements are not routinely taken
- vi) Small wards

-

³ Because of the potential confusion that arises in this observational study where we observe nurses taking observations, we will use the term 'vital signs measurement' and 'vital signs rounds' etc. to refer to nurses making vital signs observations of patients. The term 'observation' will be used for researchers' observation of nursing care.

At each Trust, we will ask the local PI to identify all eligible wards to take part in the study. We will also ask them to collate basic profile information to describe Trust and ward level policies / practices relating to vital signs measurement and to determine willingness to take part.

We will randomly select 4 wards from each Trust which to undertake the research and initially we will consent ward managers to take part. If a selected ward manager does not consent we will randomly select another ward.

We will organise a meeting with the ward manager for each ward and provide detail about the study. We will also use this meeting to gain more information and to characterise in detail the approach to taking vital signs measurement in each participating ward (e.g. use of EWS and local protocols, scheduled or customary observation rounds, staff who undertake vital signs measurements). Where we have access to electronic vital signs observation data we will use this to identify patterns of vital signs measurement in the participating wards.

For each ward we will undertake 8 hours of observations in 4 sessions, aiming to capture at least 10 sets of vital signs measurements per 2 hour session. This will result in a *minimum* sample of 640 (4 sessions x 4 wards x 4 hospitals X 10) sets of observations. Based on these preliminary investigations, we will define observation schedules for each ward *a priori* designed in order to estimate the nursing time involved in taking a representative sample of observations and aiming to observe a range of staff and both 'responsive' (scheduled according to individual patient need) and routine (rounds) vital signs measurement. Where vital signs rounds mean that activities are clustered at specific times of day we will split observation sessions in order to capture more than one round on the same day where feasible.

During the observation sessions, we will seek to recruit all nurses working on the ward. Explicit consent will be gained on behalf of staff from the ward manager who agrees to take part. All staff on shifts chosen for observation sessions will be given clear opportunity to opt out and so individual consent will be implied & recorded, based on ward rosters.

Patients and relatives will be informed about the study through posters displayed on the ward, information leaflets distributed during sessions and personal explanations by the researcher and / or nurse being observed where relevant. No personal information will be collected from or about patients although basic contextual information that can be readily observed will be recorded, for example the patient's position and presence of relatives while the vital signs measurements are being taken.

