2.4.3.6 Data analysis

We aim to estimate the time taken to undertake vital signs observations and to understand systematic sources of variation that may influence the 'burden' of vital signs observations. We will determine the extent to which estimates of time taken

are sensitive to predictable factors and use this as the basis of a sensitivity analysis when estimating associated costs.

Our data will consist of a series of interactions that represent a complete set of vital signs measurements. Measurements will be grouped into rounds, where one or more sets of vital signs observations and associated actions are recorded. Additionally, there may be other actions associated with vital signs measurement that we are not able to record because they do not occur within vital signs rounds.

We will estimate the time taken for vital signs measurement in 2 ways.

- Average time to take a set of observations (based on individual sets of measures)
- ii) Average length of vital signs rounds / number of sets of vital signs measurements taken with the round

We will use multilevel mixed-effects models to determine the influence of patient, nurse, ward and hospital factors on the length of observation. Factors considered will include the average number of measurements taken in a round in order to identify efficiencies that may be associated with undertaking formal observation rounds. The coefficients from these models will be used to estimate adjusted (conditional) mean work (time) associated with taking observations based upon these factors. We will use our stakeholder consultations (see main protocol) in order to identify whether any further allowances should be added to estimated times based on unobserved work associated with vital signs measurements. These factors and the differences between estimated values will be used in sensitivity analyses in the economic analysis (below)

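### The four wards per Trust are drawn without regard to ward type, so the medical/surgical mix within a Trust is left to chance; drawing within type would be a cheap improvement

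*Protocol*

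**What the plan says.** Section 2.4.3.1 of the protocol places the prospective study in "16 adult general wards at 4 acute general NHS hospital Trusts". Two Trusts record electronically, and two that still use paper are to be sought.

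Section 2.4.3.2 then sets the sampling of wards:
- The frame is one list covering both types: "Eligible wards are those classified as adult general (medical / surgical) wards". At each Trust, "we will ask the local PI to identify all eligible wards to take part in the study".
- The draw is stated as "We will randomly select 4 wards from each Trust". No stratum, quota or balancing rule by ward type is given.
- Refusals are handled in the same way: "If a selected ward manager does not consent we will randomly select another ward".
- The load is fixed per ward: "For each ward we will undertake 8 hours of observations in 4 sessions", giving a minimum "sample of 640 (4 sessions x 4 wards x 4 hospitals X 10) sets of observations".

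The variety sought in that section concerns the choice of the two extra Trusts. The schedules set in advance concern sessions on wards already drawn. Neither balances ward type.

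Section 2.4.3.6 plans multilevel models to "determine the influence of patient, nurse, ward and hospital factors" on the length of an observation. The coefficients are then used for adjusted mean times and for sensitivity analyses of cost.

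**The concern.** With four wards per Trust, an unrestricted draw can easily return three or four wards of one type. A Trust whose four wards are all medical contributes nothing within that Trust to a medical/surgical comparison, and its ward-type effect cannot be told apart from its Trust effect. Because recording mode is a Trust-level attribute, some of that entanglement carries over to recording mode.

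The model in section 2.4.3.6 is meant to attribute variation in time to ward and hospital factors, and it has 16 wards in four Trusts with which to do so. The draw happens before any analysis, so no later analysis plan can restore a contrast that the sample does not contain.

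**Working it through.** **Inputs from the protocol.** 4 Trusts, 4 wards per Trust, 4 sessions and 8 hours per ward, at least 10 sets per session (sections 2.4.3.1 and 2.4.3.2).

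**The plan's own figure.** 4 sessions × 4 wards × 4 hospitals × 10 sets = 640, which reproduces. Total observation time is 16 × 8 = 128 hours. The ±10% precision in section 2.4.3.4 cannot be reproduced, because its standard errors come from a cited study.

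**Assumed inputs.** The size of the eligible list and its medical:surgical split are not given. Section 2.4.1.1 mentions about 32 and 58 general wards at the two core Trusts, before this study's exclusions, so lists of 12 to 58 are tried.

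**Step 1: chance that a Trust's four wards are all one type.** With M medical and S surgical wards on the list, p = [C(M,4) + C(S,4)] / C(M+S,4). For four Trusts with the same list, the chance of at least one such Trust is 1 − (1 − p)^4.

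| List (M:S) | p per Trust | At least one of 4 Trusts |
|---|---|---|
| 12 (6:6) | 6.1% | 22% |
| 12 (8:4) | 14.3% | 46% |
| 18 (12:6) | 510/3060 = 16.7% | 52% |
| 20 (10:10) | 420/4845 = 8.7% | 30% |
| 20 (14:6) | 21.0% | 61% |
| 32 (16:16) | 10.1% | 35% |
| 32 (24:8) | 29.7% | 76% |
| 58 (29:29) | 11.2% | 38% |
| 58 (41:17) | 24.4% | 67% |

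More uneven lists give higher values (20 wards split 16:4: 37.6%).

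**Step 2: information lost on a ward-type contrast.** With Trust in the model and equal effort per ward, the within-Trust information is proportional to n1·n2/4, where n1 and n2 are the wards of each type drawn. It is 1 for a 2-2 split, 0.75 for 3-1 and 0 for 4-0.
- 10:10 list: 2-2 has probability 2025/4845 = 0.418, 3-1 either way 2400/4845 = 0.495, 4-0 either way 0.087. Expected information = 0.418 + 0.75 × 0.495 = 0.79, a loss of about 21% against 2+2.
- 12:6 list: 2-2 has probability 990/3060 = 0.324, 3-1 either way (1320 + 240)/3060 = 0.510, 4-0 either way 0.167. Expected information = 0.324 + 0.75 × 0.510 = 0.71, a loss of about 29% against 2+2.

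**Step 3: price of drawing within type, for the overall mean.** The variance factor is the sum over types of W²/a, with W the type's share of the list and a its share of the sample. Equal variance within each type is assumed.
- 2+2 on an even list: 1.00.
- 3+1 on a 75:25 list: 1.00; on a 70:30 list: 1.01.
- 2+2 weighted to a 12:6 list: (4/9 + 1/9)/0.5 = 1.11.
- 2+2 weighted to a 70:30 list: (0.49 + 0.09)/0.5 = 1.16, so an illustrative ±10% becomes 10 × √1.16 = ±10.8%.
- 2+2 weighted to an 80:20 list: (0.64 + 0.04)/0.5 = 1.36, or about ±11.7%.

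**The case against.** The best defence is that a random draw is a sound design and that the protocol's only precision target, in section 2.4.3.4, is an overall mean time. No medical/surgical contrast in time is named. Section 2.4.3.6 lists ward factors only in general terms, and the medical and surgical comparisons in sections 2.3 and 2.4.4 concern deterioration risk. That stands, and it keeps the point minor.

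A reader might go on to infer several stronger things that the protocol does not support:
- **That the overall mean is biased.** It is not. An uneven split in the realised sample is ordinary sampling error between wards.
- **That ward type is confounded with recording mode.** If two Trusts use each mode, there are eight wards per mode. The chance that all eight wards of a given mode are one type is 2 × 0.0433² = 0.4% with 10:10 lists and about 2.6% with 12:6 lists. The figures for at least one Trust in four describe a weakened contrast, not one that cannot be estimated.
- **That the cost model carries times to wards of a similar type.** In section 2.4.5, similar wards supply the NEWS profile, and hence the number of observations.
- **That every 3-1 split is a poor sample.** On a 12:6 list the split is 3-1 or worse in 68% of draws, but three medical and one surgical is the closest possible to proportional (2.67:1.33) and alone accounts for 1320/3060 = 43%.
- **That ward type is already on file, so that stratifying is free.** The profile in section 2.4.3.2 covers vital-signs policies, practices and willingness, not specialty. The section also admits that adult general wards have no precise agreed definition. A fixed 2+2 draw from an uneven list costs precision, as Step 3 shows.

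**Conclusion.** The point holds as a minor design improvement. It is not an error in any stated figure. The unrestricted draw and replacement are unbiased for the overall mean but leave ward type within a Trust to chance. For the assumed lists in the table, a Trust's four wards are all one type with probability about 6% to 30%. The expected loss of within-Trust information on a ward-type contrast, relative to 2+2, is about 21% (10:10) to 29% (12:6). With 16 wards, that makes ward and hospital factors harder to separate in the planned model.

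All of this rests on assumed list sizes and splits, on each ward being classifiable by type, and on equal effort per ward. The gain for the overall mean is unknown, because the protocol does not say that time per set differs by ward type.

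**What to change.** Amend section 2.4.3.2 as follows:
1. Ask the local PI to record ward type on the eligible list: medical, surgical, or mixed, with a stated rule for mixed wards.
2. Draw the four wards at random within type in each Trust, close to proportionate to the list, with at least one of each type where both exist (2+2 where the list is about even).
3. Replace a refusing ward by a random draw from the same type.
4. Weight to the list when reporting an overall mean if the allocation is not proportionate.

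The 16 wards, 128 hours and minimum of 640 sets are unchanged, and the one-type outcome disappears wherever both types are listed and a same-type replacement is available. The cost is one extra field and the mixed-ward rule. On uneven lists there is a choice to make. A 3+1 draw fixes the within-Trust information at 0.75 of the 2+2 value, so on a 12:6 list it mainly removes the zero-information outcome and raises the average only from 0.71. A 2+2 draw there recovers the full contrast, but it needs weights and has a variance factor for the overall mean of about 1.11 (1.16 at 70:30).

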2.4.3.3 Observation session

Observations will be undertaken by one or more trained researchers, who will act as non-participant observers. They will position themselves to be able to discreetly observe a group of patients whose vital signs observations will fall due, or else discreetly shadow a nurse who is about to undertake a vital signs observation round. We will adapt tools and techniques from the HS&DR funded 'CLECC' study [25] and Wong et al.[26] Data will be recorded on a tablet device using software designed for recording nurse patient interactions on wards (QITool) with records taken at both the session level and the 'interaction' level (in this case a set or group of vital signs measurements). For each observation session we will record the number of patients and the number and grades (RN band 5 and above, HCA and other assistant staff

band 1-4) of all nursing care staff on the ward. For each patient whose vital signs are recorded we will assign a session-specific identifier and record basic details that can be discerned from distant observation, such that would be available to any visitor to the ward (for example position and the presence of visitors). The type of staff taking vital signs measurements will be recorded and categorised (e.g. registered nurse, care assistants).

We will record start and finish times for both vital signs rounds and individual vital signs measurements. For a vital signs 'round' an interaction record will be opened with a start time recorded when the nurse begins to assemble the necessary equipment and ended when the nurse moves away from the patient bed space and engages on another task (i.e. other than taking vital signs measurements from the next patient) unrelated to vital signs measurements. Therefore, each set vital signs measurements will be clustered with a vital signs 'round' which will include one of more sets of vital signs measurements. Observation sessions will continue for 2 hours with observer discretion to extend the session if the required number of vital signs measurements have not been recorded.

Observers will not intervene in care but should they observe practice that risks causing the patient harm they will alert the nurse in charge.

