2.4.3.5 Observer training

The observer will be trained prior to undertaking observations using protocols and training material from Wong et al[26] and the QITool. We will also undertake intermittent reliability tests to ensure there is no deterioration in observer performance over time. Although we cannot easily discount the effects of observers on nurses' performance of vital signs measurements, we will seek to undertake observations in as unobtrusive fashion as possible and emphasise to participating staff that we are not evaluating their practice.

It seems most likely that observer effects will increase diligence, which may lead to increased estimates of the time taken to obtain vital signs measurements. For those hospitals using electronic vital signs recording, we will analyse the routine data obtained from the retrospective analysis, by looking for evidence that incomplete observations were less frequent during observation periods. We will consider the potential implications of any observer effects through sensitivity analysis in our economic modelling

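### The nurse being timed may also explain the study to patients, and any explanation given at the bedside during a round is counted as vital signs work, so the time and cost estimates can be biased upward

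*Protocol*

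**What the plan says.** **Informing patients (Protocol 2.4.3.2).** Patients and relatives learn of the study from posters, from "information leaflets distributed during sessions and personal explanations". The explanations may come from two sources: "personal explanations by the researcher and / or nurse being observed where relevant". The nurse whose work is being timed is thus one of the people who may explain the study.

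**Timing (2.4.3.3).** "We will record start and finish times for both vital signs rounds and individual vital signs measurements". The clock rule is spelled out for rounds only. A round has its "start time recorded when the nurse begins to assemble the necessary equipment" and is "ended when the nurse moves away from the patient bed space and engages on another task", where the other task must be unrelated to vital signs. No pause or deduction for study-related talk is stated, and no start or stop event is given for an individual set.

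**Use of the times.** Section 2.4.3.6 estimates (i) the mean time per individual set and (ii) round length divided by the number of sets in the round. Section 2.4.5 multiplies time per observation by number of observations and by unit staff cost.

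**Observer effects (2.4.3.5).** The protocol expects that being watched may lengthen the measured times, through greater diligence. It plans one empirical check, at hospitals with electronic recording: whether incomplete sets were less frequent during observation periods. It also plans a sensitivity analysis of observer effects in the economic model.

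**The concern.** The study aims to measure how long nurses spend on vital signs, yet its own procedure allows the measured nurse to take on an additional task that exists only because of the study. If that task is done at a bedside during a round, the stated clock rule does not remove it. The resulting error has one sign, so it does not average out over sets, wards or hospitals. The planned precision in 2.4.3.4 is based on standard errors and does not cover it. Nor can the check on incomplete sets reveal it, because talking about the study does not change how many vital signs are recorded.

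At stake are the mean time per set and the absolute staffing costs built on it. Study talk that is not marked when it happens cannot be recovered at the analysis stage.

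**Working it through.** **1. The plan's own figures.** Minimum sample: 4 sessions x 4 wards x 4 hospitals x 10 sets = 640, as stated in 2.4.3.2. Total observation time is 16 wards x 8 h = 128 h, so the minimum yield allows at most 128 x 60 / 640 = 12 minutes of session time per set. The precision of about +/-10% in 2.4.3.4 cannot be reproduced, because the standard errors and mean times of the cited time study are not given.

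**2. Is bedside study talk inside the timed interval?**
- *Measure (ii), rounds.* The round closes only when the nurse has left the bed space and has also started an unrelated task. A nurse who explains the study while still at the bed meets neither the first condition nor both together, so the time stays in the round. This follows from the text.
- *Measure (i), individual sets.* Start and finish are recorded but their defining events are not stated. Inclusion is possible and is not shown.
- *Explanations outside a round.* One given before equipment is assembled, or given by the researcher, adds nothing by this route.

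**3. Size.** Let p be the share of sets with an explanation inside the timed interval, e its length, and m the true mean time per set. Then

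relative bias = p x e / m.

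The protocol gives none of p, e or m. All three are assumptions here, with m from 3 to 6 minutes and e from 15 to 60 seconds.

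| p | e | m = 3 min | m = 4 min | m = 5 min | m = 6 min |
|---|---|---|---|---|---|
| 10% | 15 s | 0.8% | 0.6% | 0.5% | 0.4% |
| 25% | 30 s | 4.2% | 3.1% | 2.5% | 2.1% |
| 50% | 60 s | 16.7% | 12.5% | 10.0% | 8.3% |

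For example, 0.10 x 15 / 300 = 0.5%; 0.25 x 30 / 300 = 2.5%; 0.50 x 60 / 300 = 10%.

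**4. What it takes to reach 10%.** Setting p x e / m = 0.10 gives p = 0.10 x m / e.
- e = 30 s: p = 18/30 = 60% of sets at m = 3 min, and 30/30 = 100% at m = 5 min.
- e = 60 s: p = 18/60 = 30% at m = 3 min, and 30/60 = 50% at m = 5 min.

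**5. Effect on costs.** Staffing cost is time x number x unit cost, so a relative bias b in time is the same relative bias in cost. If b is the same for every regimen, the cost ratio (1+b)C1 / [(1+b)C0] = C1/C0 and the ranking by staffing cost are unchanged. The absolute costs scale by (1+b), and so does the cost difference: (1+b)C1 - (1+b)C0 = (1+b)(C1 - C0).

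**The case against.** The strongest answer is that the protocol permits nurse explanations but does not require them. They are conditional, the researcher is an alternative source, and the phrase about sessions is attached to the leaflets. Explanations could all take place before a round begins. This stands. A reader might infer that study talk does fall inside the timed sets and does inflate both measures, but the text supports only that it can enter rounds and might enter sets.

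Second, the recording tool and the training material are not shown and may already tell observers how to treat interruptions. That is possible. The protocol's description of the records cannot be taken as a full field list, so one cannot say that no field would capture such talk.

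Third, 2.4.3.5 already expects an upward observer effect and promises a sensitivity analysis. That partly stands, since varying the time per set would span a shift of this kind. Diligence is the only mechanism named, however, and without a record of how often study talk occurred the range would be a guess.

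A reader might also see a contradiction between giving out leaflets and researchers "who will act as non-participant observers". That reading is weak. Handing over a leaflet is not taking part in care, and 2.4.3.5 promises only that "we will seek to undertake observations in as unobtrusive fashion as possible".

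Finally, noting study talk is harder than it sounds. Observers keep their distance and may not hear what is said, so subtracting seconds would be unreliable. This stands and shapes the fix.

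**Conclusion.** The point holds as an avoidable measurement risk. It is not an error in any stated figure, and the 640 sets are unaffected. The protocol lets the timed nurse explain the study, and the round clock keeps any bedside explanation in round time per set. From there it passes in proportion into absolute staffing costs. Inclusion in the individual set time is possible but not established, because its boundaries are undefined.

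The bias cannot be negative and does not shrink with more sets. Its size is not determinable from the protocol. On the assumed inputs it is below 1% when explanations are rare and short, and about 2% to 4% when a quarter of sets contain 30 seconds. A reader might conclude that it uses up the whole planned +/-10%, but the documents do not support that. At 5 minutes per set it would need half of all sets to contain a full minute of study talk. The case for acting is the low cost of the change, not a demonstrated large bias.

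**What to change.** In Protocol 2.4.3.2, state that:
- the researcher gives leaflets and explanations to patients and visitors in the observed area before timing starts, or between rounds for new arrivals;
- observed staff refer study questions to the researcher and do not explain the study during a timed set or round.

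In 2.4.3.3, add that the observer flags any set or round in which study talk evidently occurs. In 2.4.3.6, add a sensitivity analysis that excludes the flagged records. A flag is preferable to subtracting seconds, given the observer's distance. Exclusion belongs in a sensitivity analysis, because sets in which patients ask questions may differ from the rest in other ways.

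The cost is a few minutes of researcher time per session, one marker in the tablet record, some patients informed slightly later, and possibly a minor amendment to the patient information procedure. The sample size and the rest of the design stay as they are.
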